## **SUMMARY OF CHANGES – Protocol**

### **I. Response to a RRA from Dr. [REDACTED], dated 09/29/2023:**

| #  | Section                                     | Comments   |
|----|---|--|
| 1. | Header,
Title Page       | Updated protocol version.  |
| 2. | 7.1.2 , 7.3 | Updated instructions for managing specific AEs for Atezolizumab. |
| 3. | 10.1.1.1                    | Revised Atezolizumab CAEPR.                                      |

## SCHEMA

### Stratification Factor:

Site of Disease (Gallbladder cancer (GBC) vs. Intrahepatic cancer (IHC) vs. Extrahepatic cholangiocarcinoma (EHC))

## 1. OBJECTIVES

### 1.1 Primary Objectives

- 1.1.1 To assess the response rate (ORR) of patients with unresectable, pre-treated biliary cancers treated with the combination of atezolizumab and CDX-1127 (varlilumab) with or without cobimetinib.
- 1.1.2 To assess the progression free survival (PFS) of patients with unresectable, pre-treated biliary cancers treated with the combination of atezolizumab and CDX-1127 (varlilumab) with or without cobimetinib

### 1.2 Secondary Objectives

- 1.2.1 To assess the safety and tolerability of combination of atezolizumab and CDX-1127 (varlilumab) with or without cobimetinib in patients with unresectable, pre-treated biliary cancers.
- 1.2.2 To assess overall survival (OS) of patients with unresectable, pre-treated biliary cancers treated with the combination of atezolizumab and CDX-1127 (varlilumab) with or without cobimetinib.
- 1.2.3 To determine the effect of combination atezolizumab and CDX-1127 (varlilumab) +/- cobimetinib on T cell subpopulations systemically and intratumorally.

[REDACTED]

1.3.1 [REDACTED]

1.3.2 [REDACTED]

1.3.3 [REDACTED]

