## 9. STATISTICAL CONSIDERATIONS

### 9.1 Study Design/Endpoints

The proposed study is an open-label, randomized phase 2 trial evaluating atezolizumab in combination with CDX-1127 (varlilumab) with or without the addition of cobimetinib in unresectable, pre-treated cholangiocarcinoma. Patients will be randomized in a 1:1 ratio to the two arms. The primary objective of the trial is to determine whether the combination of checkpoint blockade with an immune co-stimulatory yields a clinically compelling antitumor activity (measured as overall response rates [ORR, assessed by RECIST 1.1] and progression free survival [PFS, assessed by RECIST 1.1]) and if this effect can be further amplified with the addition of MEK inhibition. Secondary endpoints include safety, overall survival (OS), immunologic correlates, and pharmacokinetics of atezolizumab and varlilumab. Objective response (OR) and PFS are co-primary endpoints.

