##### Progression Free Survival (PFS):

PFS is defined as the duration of time from date of randomization to time of progression or death. This analysis is intent-to-treat including all randomized patients. Patients who come off of study treatment for clinical progression without radiographic progression (i.e. clinical progression) will be coded as progression for the analysis, and the date of progression is the date of clinical progression. Due to the rapid progression of the disease in the majority of patients, little loss to follow up is expected, but subjects who are lost to follow-up as of the data analysis cutoff date will be right-censored. The censoring date will be determined from the date the subject was last evaluated for progression. PFS within each treatment arm will be summarized descriptively using Kaplan-Meier plots, and compared between arms using log-rank tests.

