### 9.4 Analysis of Secondary Endpoints

#### Clinical Secondary Endpoints:

##### Overall survival (OS)

OS is defined as the duration of time from start of study treatment to time of death. For subjects lost to follow-up or whose vital status is unknown, every effort will be made to determine the date such subjects were last known to be alive. Such efforts may include phone calls, certified mail, and the checking of public records. Subjects who are alive or lost to follow-up as of the data analysis cutoff date will be right-censored. The censoring date will be determined from the date the subject was last known to be alive. OS will be summarized descriptively using the Kaplan-Meier method. The analysis of OS will be performed on all randomized patients, as well as all the individuals who complete at least one dose of therapy. Median OS will be reported and the associated 95% confidence interval will be estimated.

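### Overall survival is given no between-arm estimate in this randomised trial; an estimation-only hazard ratio by regimen would be a nearly free improvement

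*Combined protocol and SAP*

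**What the plan says.** Objective 1.2.2 is "To assess overall survival (OS) of patients with unresectable, pre-treated biliary cancers treated with the combination of atezolizumab" and varlilumab, with or without cobimetinib. Objective 1.1.2 frames PFS in the same way. Section 9.1 states the design: "The proposed study is an open-label, randomized phase 2 trial", and "Patients will be randomized in a 1:1 ratio to the two arms". Part of the primary objective there is "if this effect can be further amplified with the addition of MEK inhibition".

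The OS analysis is in section 9.4: "OS will be summarized descriptively using the Kaplan-Meier method", and "Median OS will be reported and the associated 95% confidence interval will be estimated". On population, "The analysis of OS will be performed on all randomized patients", and also on those who complete at least one dose. The text names no hazard ratio, test or difference, and does not say that the summary is by arm. Section 12.2.1 adds only a definition of OS.

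For PFS, section 9.1 (repeated in 12.1.6) goes further: "PFS within each treatment arm will be summarized descriptively using Kaplan-Meier plots, and compared between arms using log-rank tests". Section 9.2 makes that comparison conditional on both arms meeting the response criterion.

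**The concern.** Patients are randomised so that the contribution of cobimetinib can be estimated without confounding. For OS the plan does not use that randomisation. Other endpoints get more: section 9.4 tests the CD8+ T-cell change between arms and relates OS to antibody clearance, but does not relate OS to randomised treatment.

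Two features of the PFS comparison make this matter.

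- PFS involves judgement made with the regimen known. It counts clinical progression without radiographic progression (9.1, 12.1.6), and no blinded independent review is described. Death is ascertained objectively, so an OS estimate would be a useful companion.
- The PFS comparison may not be run. Response is judged separately in each arm by a two-stage rule, and if either arm fails, section 9.2 does not call for the comparison. The background (2.3.1) shows that this is realistic. In the predecessor trial of atezolizumab with or without cobimetinib, median PFS was 3.65 versus 1.87 months, with one partial response in each arm.

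In that situation the report would contain no planned between-arm efficacy estimate. A reader could at best compare two median OS values by eye.

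**Working it through.** **Inputs from section 9.2.** 64 patients, 32 per arm; 55 PFS events; HR 0.5; one-sided alpha 0.10; 90% power; two-stage rule of 18 then 14 patients per arm (stop at 0 responses in 18; pass at 4 or more in 32); response rates 5% and 20%. No OS effect size, number of deaths or OS power appears anywhere, so deaths are an assumption: 40 to 55.

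**1. The plan's own figures.** Schoenfeld events with 1:1 allocation: 4 × (1.2816 + 1.2816)² / (ln 0.5)² = 4 × 6.570 / 0.4805 = 54.7, so 55, with power 0.901. This matches. For the response rule, early stopping at 5% is 0.95^18 = 0.397 (stated 0.4).

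**2. How often the PFS comparison is reached.** P(arm passes) is the sum over x = 1 to 18 of P(X1 = x) × P(X2 ≥ 4 − x), with X1 binomial on 18 and X2 binomial on 14. This is 0.0721 at a true rate of 5% and 0.9015 at 20%. With independent arms:

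| True response rates | P(both arms pass) |
|---|---|
| 20% and 20% | 0.9015² = 0.81 |
| 20% and 5% | 0.9015 × 0.0721 = 0.065 |
| 5% and 5% | 0.0721² = 0.005 |

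**3. Precision of an OS hazard ratio.** SE(log HR) = 2/√d for d deaths, and the 95% CI factor is exp(1.96 × 2/√d).

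| Deaths (assumed) | Factor | 95% CI if observed HR = 0.70 |
|---|---|---|
| 40 | 1.86 | 0.38 to 1.30 |
| 50 | 1.74 | 0.40 to 1.22 |
| 55 | 1.70 | 0.41 to 1.19 |

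**4. Comparison with two medians.** Under exponential survival, with censoring only after the median, Var(log median) = 1/(n (ln 2)²) per arm. For the ratio with n = 32 per arm: 2/(32 × 0.4805) = 0.130, so the SE is 0.361 and the factor is exp(1.96 × 0.361) = 2.03. Var(log HR) = 4/d, which is 0.100 at 40 deaths and 0.073 at 55. The median ratio therefore has about 1.3 to 1.8 times the variance of the log hazard ratio.

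**The case against.** The strongest reply is that this is a deliberate and ordinary choice. The trial is sized on a per-arm response rule with one powered contrast, PFS. Objective 1.2.2 says assess, not compare, and no OS effect or power is claimed. A descriptive OS summary in 64 patients is acceptable. This stands, and it is why the point is an improvement only. The verb settles little, however, because objective 1.1.2 uses the same one for PFS, which is compared.

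A second reply is that the estimate would be too imprecise to matter. Power for a true HR of 0.7 at two-sided 0.05, from Φ(|ln HR| √d/2 − 1.96), is 0.20 with 40 deaths and 0.26 with 55. That also stands, and it rules out a significance claim. It does not favour medians, which are less precise still.

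A third reply concerns stratifying by three disease sites: the PFS log-rank is not stated to be stratified, and strata may be sparse (64/3, about 21 patients each on average). Stratification follows the randomisation, so it is reasonable, but the difference from PFS should be deliberate.

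A reader might infer more than the documents support:

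- That OS is immune to the open-label design. Progression ends treatment (6.4), and treatment beyond progression depends partly on the provider's agreement (6.2). Knowledge of the regimen can therefore affect exposure and later therapy, and through them survival.
- That every death will be observed. Follow-up ends at withdrawal of consent or study closure (6.5), and section 9.4 censors patients alive or lost to follow-up.
- That OS would be pooled over arms. Section 9.4 omits the words, but the objective's wording in a two-arm trial makes by-arm reporting the natural reading.

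**Conclusion.** The gap is real but modest. Followed exactly, the plan gives no between-arm OS estimate. Because the PFS comparison is conditional, it can also leave a randomised trial without any planned between-arm efficacy estimate. With independent arms, the PFS comparison is reached with probability 0.81 if both true response rates are 20%, and 0.065 if only one is.

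It would be tempting to conclude that the plan is wrong, or that an OS hazard ratio would show whether cobimetinib helps. Neither follows. The descriptive choice is defensible, and the intervals above exclude 1 only for a large effect. What the change adds is a pre-specified, more efficient summary of data already being collected.

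The precision figures rest on the assumed 40 to 55 deaths and on both arms reaching 32 patients. If one arm closes after its first 18, roughly 36 patients have concurrent randomised comparators. Even with all 36 dead, the factor would be exp(1.96 × 2/6) = 1.92. The figure of 2.03 for medians also assumes exponential survival and censoring only after the median.

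**What to change.** In section 9.4, replace the OS summary sentences with a plan along these lines:

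- Kaplan-Meier OS curves, and medians with 95% CIs, by randomised regimen.
- The OS hazard ratio, with versus without cobimetinib, and its two-sided 95% CI, from a Cox model stratified by site of disease (the randomisation factor), in all randomised patients.
- A label of supportive estimation, with no significance claim.

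Three details need settling in the same edit.

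- Time origin. Section 9.4 starts OS at the start of treatment and section 12.2.1 at randomisation. The former is undefined for randomised but untreated patients, whom 9.4 includes. Use randomisation in both places.
- Arm names. Name the regimens. The T-cell paragraph of section 9.4 calls the cobimetinib regimen arm B, while section 6.1 and footnote D of section 11 call it arm A, so a ratio of A to B would have an ambiguous direction.
- Early closure. If one arm stops after stage 1, say that the contrast uses patients randomised while both arms were open.

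The cost is a few sentences and one model on data already collected, written before outcomes are seen. No patients or visits are added.

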## 2. BACKGROUND

### 2.1 Study Disease(s)

Biliary Tract Cancer (BTC) refers to a group of heterogenous malignancies arising from biliary epithelial cells along different sites of the biliary tree that include intrahepatic cholangiocarcinoma (ICC), extrahepatic cholangiocarcinoma (ECC), and gallbladder cancer (GBC). Overall survival for this disease, even when including resectable patients, is poor with less than 5% of patients living beyond 5 years (Shaib and El Serag, 2004). Unresectable CCA patients treated with standard frontline therapy, gemcitabine plus cisplatin, have a median overall survival (OS) of less than one year (Valle *et al.*, 2010). The benefit of cytotoxic chemotherapy in the second line setting is small, underscoring the need for additional treatment options for these patients (Lamarca *et al.*, 2014; Rogers *et al.*, 2014; Lamarca *et al.*, 2019). Inhibition of programmed cell death protein 1 (PD-1) or its ligand (PD-LD1) has shown limited clinical activity in BTC as monotherapy, with response rates of approximately 5-11% in the largest reported prospective clinical trials (Ueno *et al.*, 2019; Ioka *et al.*, 2019; Ueno *et al.*, 2018; Kim *et al.*, 2020). The development of novel therapeutic combinations that can extend the clinical benefit of ICIs to immunologically resistant tumors such as BTC remains a significant challenge.

### 2.2 CTEP IND Agents

#### 2.2.1 Atezolizumab

Atezolizumab is a human immunoglobulin (Ig) G1 monoclonal antibody consisting of two heavy chains (448 amino acids) and two light chains (214 amino acids) and is produced in Chinese hamster ovary cells (Investigator's Brochure, 2016). Atezolizumab was engineered to eliminate Fc-effector function via a single amino acid substitution (asparagine to alanine) at position 298 on the heavy chain, which results in a non-glycosylated antibody that has minimal binding to Fc receptors, thus eliminating detectable Fc-effector function and associated antibody-mediated clearance of activated effector T cells. Atezolizumab targets human programmed death-ligand 1 (PD-L1) and inhibits the interaction with its PD-L1 and its receptors, PD-1 and B7-1 (also known as CD80), both of which function as inhibitory receptors expressed on T cells.

Atezolizumab shows anti-tumor activity in both nonclinical models and cancer patients and is being investigated as a potential therapy in a wide variety of malignancies. Atezolizumab is being studied as a single agent in the advanced cancer and adjuvant therapy settings, as well as in combination with chemotherapy, targeted therapy, and cancer immunotherapy.

Atezolizumab is approved in the United States for the treatment of locally advanced or metastatic urothelial carcinoma and as well as metastatic non-small cell lung carcinoma.

##### 2.2.1.1 Mechanism of Action

PD-L1 expression is prevalent in many human tumors (*e.g.*, lung, bladder, ovarian, melanoma, colon carcinoma), and its overexpression has been associated with poor prognosis in patients with several cancers (Thompson *et al.*, 2006; Hamanishi *et al.*, 2007; Okazaki and Honjo 2007;

Hino *et al.*, 2010). PD-L1 binds to two known inhibitory receptors expressed on activated T cells (PD-1 and B7.1), and receptor expression is sustained in states of chronic stimulation such as chronic infection or cancer (Blank *et al.*, 2005; Keir *et al.*, 2008). Ligation of PD-L1 with PD-1 or B7.1 inhibits T-cell proliferation, cytokine production, and cytolytic activity, leading to the functional inactivation or inhibition of T cells. Aberrant expression of PD-L1 on tumor cells has been reported to impede anti-tumor immunity, resulting in immune evasion (Blank and Mackensen, 2007). Therefore, interruption of the PD-L1/PD-1 and PD-L1/B7.1 pathway represents an attractive strategy to reinvigorate tumor-specific T-cell immunity.

Blockade of PD-L1 or PD-1 with monoclonal antibodies has been reported to result in strong and often rapid antitumor effects in several mouse tumor models (Iwai *et al.*, 2002; Strome *et al.*, 2003). These data suggest that tumor-specific T cells may be present in the tumor microenvironment in an inactive or inhibited state, and blockade of the PD-L1/PD-1 pathway can reinvigorate tumor-specific T-cell responses.

Collectively, these data establish the PD-L1/PD-1 pathway as a promising new therapeutic target in patients with advanced tumors. Immune-related adverse events (AEs) reported from the two recent studies were consistent with the role of the PD-L1/PD-1 pathway in regulating peripheral tolerance.

#### 2.2.1.2 Summary of Nonclinical Experience

The safety, pharmacokinetics (PK), and toxicokinetics of atezolizumab were investigated in mice and cynomolgus monkeys to support intravenous (IV) administration and to aid in projecting the appropriate starting dose in humans. Given the similar binding of atezolizumab for cynomolgus monkey and human PD-L1, the cynomolgus monkey was selected as the primary and relevant nonclinical model for understanding the safety, PK, and toxicokinetics of atezolizumab.

Overall, the nonclinical PK and toxicokinetics observed for atezolizumab supported entry into clinical studies, including providing adequate safety factors for the proposed phase 1 starting doses. The results of the toxicology program were consistent with the anticipated pharmacologic activity of down-modulating the PD-L1/PD-1 pathway and supported entry into clinical trials in patients.

Refer to the Atezolizumab Investigator's Brochure for details on the nonclinical studies.

#### 2.2.1.3 Summary of Clinical Experience

A summary of clinical data from company-sponsored atezolizumab trials is presented below. Details of all ongoing studies can be found in the Atezolizumab Investigator's Brochure.

##### 2.2.1.3.1 Clinical PK and Immunogenicity

On the basis of available preliminary PK data (0.03–20 mg/kg), atezolizumab shows linear PK at doses  $\geq 1$  mg/kg (Investigator's Brochure, 2016). Based on an analysis of exposure, safety, and efficacy data, the following factors had no clinically relevant effect: age (21–89 years), body

weight, gender, positive ATA status, albumin levels, tumor burden, region or ethnicity, renal impairment, mild hepatic impairment, level of PD-L1 expression, or ECOG status. No formal PK drug-drug interaction studies have been conducted with atezolizumab, and the interaction potential is unknown. Further details can be found in the current Investigator's Brochure.

The development of anti-therapeutic antibodies (ATAs) has been observed in patients in all dose cohorts and was associated with changes in PK for some patients in the lower dose cohorts (0.3, 1, and 3 mg/kg) (Investigator's Brochure, 2016). Patients dosed at  $\geq 10$  mg/kg maintained  $C_{\min}$  values well above the target serum concentration of 6 mcg/mL despite the detection of ATAs. Accordingly, the development of detectable ATAs does not appear to have a clinically significant impact on PK for doses above 10 mg/kg. To date, no relationship between the development of measurable ATAs and safety or efficacy has been observed.

#### 2.2.1.3.2 Clinical Safety Summary

As of May 10, 2016, atezolizumab has been administered (alone or in combination with other agents) to approximately 6053 patients with solid tumors and hematologic malignancies (Investigator's Brochure, 2016). The first-in-human monotherapy study PCD4989g (in patients with locally advanced or metastatic solid tumors or hematologic malignancies) provides the majority of monotherapy safety data, with 629 safety-evaluable patients as of the data extraction date. Currently, no maximum tolerated dose (MTD), no dose-limiting toxicities (DLTs), and no clear dose-related trends in the incidence of AEs have been determined.

Fatigue, decreased appetite, nausea, diarrhea, constipation, and cough were commonly reported AEs in single and combination therapy (Investigator's Brochure, 2016). AE profiles are similar across tumor types studied, including non-small cell lung cancer (NSCLC), renal cell carcinoma (RCC), triple-negative breast cancer (TNBC), and urothelial carcinoma (UC), and are consistent with the mechanism of action of atezolizumab. The overall immune-mediated AEs reported were considered moderate in severity, and the majority of patients were able to continue on atezolizumab therapy.

As of the data extraction date of December 15, 2015, there were 629 safety-evaluable patients from the first-in-human phase 1a study PCD4989g (Investigator's Brochure, 2016). The median age was 61 years. Of the 629 patients, 619 patients (98.4%) reported at least one AE of any grade or attribution to atezolizumab, and 316 patients (50.2%) experienced at least one grade 3 or 4 AE of any attribution. A total of 444 patients (70.6%) reported at least one treatment-related AE, and 86 patients (13.7%) experienced at least one treatment-related grade 3 or 4 AE. The most frequently observed AEs of any grade and attribution (occurring in  $\geq 10\%$  of treated patients) include fatigue, decreased appetite, nausea, pyrexia, constipation, cough, dyspnea, diarrhea, anemia, vomiting, asthenia, back pain, headache, arthralgia, pruritus, rash, abdominal pain, insomnia, peripheral edema, and dizziness.

Serious AEs (SAEs) have been reported in 261 patients (41.5%) in study PCD4989g (Investigator's Brochure, 2016). Reported SAEs were consistent with the underlying disease. Treatment-related SAEs (57 patients [9.1%]) included pyrexia, dyspnea, pneumonitis, malaise, fatigue, hypoxia, colitis, and bone pain. Pooled single-agent safety data from 1978 patients with

UC, NSCLC, and other indications (including trial PCD4989g) indicate that the most frequent (>1% of patients) serious adverse drug reactions (regardless of grade) include dyspnea (3.0%), back pain (1.2%), and abdominal pain (1.1%). A list of AEs considered “expected” for atezolizumab is presented in Section 10.1.1.1.

#### 2.2.1.3.3 Immune-Related Adverse Events

Given the mechanism of action of atezolizumab, events associated with inflammation and/or immune-mediated AEs have been closely monitored during the atezolizumab clinical program (Investigator’s Brochure, 2016). To date, immune-related adverse events associated with atezolizumab include hepatitis, pneumonitis, colitis, pancreatitis, diabetes mellitus, hypothyroidism, hyperthyroidism, adrenal insufficiency, Guillain-Barré syndrome, myasthenic syndrome/myasthenia gravis, and meningoencephalitis.

For further details, see the most recent Atezolizumab Investigator’s Brochure.

#### 2.2.1.3.4 Clinical Efficacy Summary

Patients with multiple tumor types were included in study PCD4989g, with the largest cohorts consisting of patients with NSCLC, RCC, and UC (Investigator’s Brochure, 2016). Objective responses with atezolizumab monotherapy were observed in a broad range of malignancies, including NSCLC, RCC, melanoma, UC, colorectal cancer, head and neck cancer, gastric cancer, breast cancer, and sarcoma. Both the preliminary and more mature efficacy data available suggest that treatment with atezolizumab as a single agent or in combination with other therapeutic agents results in anti-tumor activity across a range of tumor types and hematologic malignancies (UC, NSCLC, RCC, TNBC, melanoma, CRC, and NHL) and across lines of therapy. Clinical benefit was observed in terms of objective responses, durability of responses, and overall survival (OS). Improved efficacy of atezolizumab was observed in the unselected patient population, as well as in patients with higher PD-L1 expression on TCs or ICs (e.g., NSCLC) or on ICs only (e.g., mUC, RCC).

